9.1 Discontinuation and completion

9.1.1 Study treatment discontinuation and study discontinuation

Discontinuation of study treatment for a participant occurs when study treatment is stopped earlier than the protocol planned duration and can be initiated by either the participant or the investigator.

The investigator must discontinue study treatment for a given participant if, he/she believes that continuation would negatively impact the participant's well-being.

Study treatment must be discontinued under the following circumstances:

- Participant/guardian decision
- Pregnancy
- Use of prohibited treatment as per the USPI

- Any situation in which study participation might result in a safety risk to the participant
- Diagnosis of PML
- Participants with active serious infections or reactivation
- Skin and/or mucosal reactions which raise the suspicion of severe generalized major skin reactions (Stevens-Johnson syndrome, or toxic epidermal necrolysis-Lyell's syndrome)
- Hypersensitivity to the study medication
- Protocol violation that results in a significant risk to the participant's safety
- Emergence of certain adverse events, such as malignancy (except successfully treated basal cell carcinoma, *in situ* squamous cell carcinoma and *in situ* carcinoma of cervix of uterus), liver failure or serious chronic infection (such as human immunodeficiency virus(HIV))
- Severe hypoproteinemia
- Non-compliance with study drug or study procedures

If discontinuation of study treatment occurs, the investigator should make a reasonable effort to understand the primary reason for the participant's premature discontinuation of study treatment and record this information.

Participants who discontinue study treatment or who decide they do not wish to participate in the study further should NOT be considered withdrawn from the study UNLESS they withdraw their consent (see Section 9.1.2 'Withdrawal of Informed Consent' section). Where possible, they should return for the EOS Visit applicable to the period in which the patient is currently in. Participants in Cohort 1 that discontinue in the Investigational Period, should return for all assessments indicated for the EOS1 Visit except for study drug administration. Participants in Cohort 1 and 2 that discontinue in the Extension Period, should return for all assessments indicated for the EOS2 Visit except for study drug administration. At EOS visits all dispensed study drug to participants in Cohort 1 and Cohort 2 should be reconciled and the adverse event and concomitant medications should be recorded on the CRF (for participants in both arms). If they fail to return for these assessments for unknown reasons, every effort (e.g. telephone, e-mail, letter) should be made to contact the participant/pre-designated contact as specified in the lost to follow-up section. This contact should preferably be done according to the study visit schedule.

If the participant cannot or is unwilling to attend any visit(s), the site staff should maintain regular telephone contact with the participant, or with a person pre-designated by the participant. This telephone contact should preferably be done according to the study visit schedule.

After study treatment discontinuation, at a minimum, in abbreviated visits, the following data should be collected at clinic visits or via telephone/email contact:

- New / concomitant treatments
- Adverse Events / Serious Adverse Events

The investigator must also contact the IRT to register the participant's discontinuation from study treatment.

9.1.2 Withdrawal of informed consent

Participants may voluntarily withdraw consent to participate in the study for any reason at any time. Withdrawal of consent occurs only when a participant:

• Does not want to participate in the study anymore,

and

Does not want any further visits or assessments

and

• Does not want any further study related contacts

In this situation, the investigator should make a reasonable effort (e.g. telephone, e-mail, letter) to understand the primary reason for the participant's decision to withdraw his/her consent and record this information.

Where consent to the use of personal and coded data is not required, participant therefore cannot withdraw consent. They still retain the right to object to the further use of personal data.

Study treatment must be discontinued and no further assessments conducted, and the data that would have been collected at subsequent visits will be considered missing.

Further attempts to contact the participant are not allowed unless safety findings require communicating or follow-up.

All efforts should be made to complete the assessments prior to study discontinuation. A final evaluation at the time of the participant's study discontinuation should be made as detailed in the assessment table.

Novartis will continue to retain and use all research results (data) that have already been collected for the study evaluation.

9.1.3 Lost to follow-up

For participants whose status is unclear because they fail to appear for study visits without stating an intention to discontinue or withdraw, the investigator must show "due diligence" by documenting in the source documents steps taken to contact the participant, e.g. dates of telephone calls, registered letters, etc. A participant should not be considered as lost to follow-up until due diligence has been completed.

9.1.4 Study stopping rules

Not applicable.

9.1.5 Early study termination by the sponsor

The study can be terminated by Novartis at any time.

Reasons for early termination may include:

- Unexpected, significant, or unacceptable safety risk to participants enrolled in the study
- Inability to complete enrollment by the end of the vaccination season
- Practical reasons

Page 40 of 51

Regulatory or medical reasons

In taking the decision to terminate, Novartis will always consider participant welfare and safety. Should early termination be necessary, participants must be seen as soon as possible for an end of study visit within 7 calendar days and treated as a prematurely withdrawn participant. The investigator may be informed of additional procedures to be followed in order to ensure that adequate consideration is given to the protection of the participant's interests. The investigator or sponsor depending on local regulation will be responsible for informing IRBs of the early termination of the trial.

9.2 Study completion and post-study treatment

Study completion is defined as when the last participant completes the EOS1 Visit if the participant will not continue into the Extension Period, or the EOS2 visit of the Extension Period if the participant continues into the extension.

10 Safety monitoring and reporting

10.1 Definition of adverse events and reporting requirements

10.1.1 Adverse events

An adverse event (AE) is any untoward medical occurrence (e.g. any unfavorable and unintended sign [including abnormal laboratory findings], symptom or disease) in a clinical investigation participant after providing written informed consent for participation in the study. Therefore, an AE may or may not be temporally or causally associated with the use of a medicinal (investigational) product.

The investigator has the responsibility for managing the safety of individual participant and identifying adverse events.

Novartis qualified medical personnel will be readily available to advise on trial related medical questions or problems.

The occurrence of adverse events must be sought by non-directive questioning of the participant at each visit during the study. Adverse events also may be detected when they are volunteered by the participant during or between visits or through physical examination findings, laboratory test findings, or other assessments.

Adverse events must be recorded under the signs, symptoms, or diagnosis associated with them, accompanied by the following information (as far as possible) (if the event is serious refer to Section 10.1.2):

1. The Common Toxicity Criteria (CTC) AE grade (1-4)

If CTCAE grading does not exist for an adverse event, use:

- 1 = mild: usually transient in nature and generally not interfering with normal activities
- 2 = moderate: sufficiently discomforting to interfere with normal activities
- 3 = severe: prevents normal activities

- 4 =life threatening
- 2. Its relationship to the study treatment. If the event is due to lack of efficacy or progression of underlying illness (i.e. progression of the study indication) the assessment of causality will usually be 'Not suspected.' The rationale for this guidance is that the symptoms of a lack of efficacy or progression of underlying illness are not caused by the trial drug, they happen in spite of its administration and/or both lack of efficacy and progression of underlying disease can only be evaluated meaningfully by an analysis of cohorts, not on a single participant
- 3. Its duration (start and end dates) or if the event is ongoing, an outcome of not recovered/not resolved must be reported
- 4. Whether it constitutes a SAE (see Section 10.1.2 for definition of SAE) and which seriousness criteria have been met
- 5. Action taken regarding with study treatment.

All adverse events must be treated appropriately. Treatment may include one or more of the following:

- Dose not changed
- Dose Reduced/increased
- Drug interrupted/withdrawn
- 6. Its outcome (not recovered/not resolved; recovered/resolved; recovered/resolved with sequelae; fatal; or unknown).

Conditions that were already present at the time of informed consent should be recorded in the source medical history of the participant.

10.1.2 Serious adverse events

An SAE is defined as any adverse event [appearance of (or worsening of any pre-existing)] undesirable sign(s), symptom(s), or medical conditions(s) which meets any one of the following criteria:

- fatal
- life-threatening

Life-threatening in the context of a SAE refers to a reaction in which the participant was at risk of death at the time of the reaction; it does not refer to a reaction that hypothetically might have caused death if it were more severe (please refer to the ICH-E2D Guidelines).

- results in persistent or significant disability/incapacity
- constitutes a congenital anomaly/birth defect
- requires inpatient hospitalization or prolongation of existing hospitalization, unless hospitalization is for:
 - routine treatment or monitoring of the studied indication, not associated with any deterioration in condition
 - elective or pre-planned treatment for a pre-existing condition that is unrelated to the indication under study and has not worsened since signing the informed consent

- social reasons and respite care in the absence of any deterioration in the participant's general condition
- treatment on an emergency outpatient basis for an event not fulfilling any of the definitions of a SAE given above and not resulting in hospital admission
- is medically significant, e.g. defined as an event that jeopardizes the participant or may require medical or surgical intervention to prevent one of the outcomes listed above

Medical and scientific judgment should be exercised in deciding whether other situations should be considered serious reactions, such as important medical events that might not be immediately life threatening or result in death or hospitalization but might jeopardize the participant or might require intervention to prevent one of the other outcomes listed above. Such events should be considered as "medically significant." Examples of such events are intensive treatment in an emergency room or at home for allergic bronchospasm, blood dyscrasias, or convulsions that do not result in hospitalization or development of dependency or abuse (please refer to the ICH-E2D Guidelines).

All new malignant neoplasms will be assessed as serious under "medically significant" if other seriousness criteria are not met and the malignant neoplasm is not a disease progression of the study indication.

Any suspected transmission via a medicinal product of an infectious agent is also considered a serious adverse reaction.

All reports of intentional misuse and abuse of the product are also considered serious adverse event irrespective if a clinical event has occurred as per Section 10.1.

10.1.3 SAE reporting

To ensure participant safety, every SAE, regardless of causality, occurring after the participant has provided informed consent and until 30 days *after the last study visit* must be reported to Novartis safety within 24 hours of learning of its occurrence. Detailed instructions regarding the submission process and requirements are to be found in the investigator folder provided to each site.

All follow-up information for the SAE including information on complications, progression of the initial SAE and recurrent episodes must be reported as follow-up to the original episode within 24 hours of the investigator receiving the follow-up information. An SAE occurring at a different time interval or otherwise considered completely unrelated to a previously reported one must be reported separately as a new event.

If the SAE is not previously documented in the Investigator's Brochure or Package Insert (new occurrence) and is thought to be related to the study treatment, a Chief Medical Office and Patient Safety associate may urgently require further information from the investigator for health authority reporting. Novartis may need to issue an Investigator Notification (IN) to inform all investigators involved in any study with the same study treatment that this SAE has been reported.

Suspected Unexpected Serious Adverse Reactions (SUSARs) will be collected and reported to the competent authorities and relevant ethics committees in accordance with EU Guidance 2011/C 172/01 or as per national regulatory requirements in participating countries.

Any SAEs experienced > 30 days after the last study visit should only be reported to Novartis Safety if the investigator suspects a causal relationship to study treatment.

Please note: The time of 30 days in the standard text above is the recommended minimum and the SAE form should be submitted to Novartis Safety. A longer duration may be appropriate for drugs with particularly long elimination half-lives or from drug classes with known late occurring effects, or when risk assessment/management objectives require prolonged safety monitoring. Please ensure the Informed Consent Form reflects this 30 day/Post Study Safety Contact.

10.1.4 Pregnancy reporting

Pregnancies

If a female trial participant becomes pregnant, the study treatment should be stopped, and the trial participant must be asked to read and sign pregnancy consent form to allow the Study Doctor ask about her pregnancy. To ensure participant safety, each pregnancy occurring after signing the informed consent must be reported to Novartis within 24 hours of learning of its occurrence. The pregnancy should be followed up on until after the Expected Due Date (EDD) to determine outcome, including spontaneous or voluntary termination, details of the birth, and the presence or absence of any birth defects, congenital abnormalities, or maternal and/or newborn complications. Additional follow up will be completed at EDD +1 month, EDD +2 months (in case no answer is received after request at EDD +1 month) and at EDD +3 months. Information on the status of the baby after delivery and information on any development issue or abnormality that would not be seen at birth must be collected.

Pregnancy should be recorded and reported on the Pregnancy Form by the investigator to the Novartis Chief Medical Office and Participant Safety (CMO&PS). Pregnancy follow-up should be recorded on the same form and should include an assessment of the possible relationship to the any pregnancy outcome. Any SAE experienced during pregnancy must be reported.

10.1.5 Reporting of study treatment errors including misuse/abuse

Medication errors are unintentional errors in the prescribing, dispensing, administration or monitoring of a medicine while under the control of a healthcare professional, participant or consumer (EMA definition).

Misuse refers to situations where the medicinal product is intentionally and inappropriately used not in accordance with the protocol.

Abuse corresponds to the persistent or sporadic, intentional excessive use of a medicinal product, which is accompanied by harmful physical or psychological effects.

Study treatment errors and uses outside of what is foreseen in the protocol will be recorded on the appropriate CRF irrespective of whether or not associated with an AE/SAE and reported to Safety only if associated with an SAE. Misuse or abuse will be collected and reported in the safety database irrespective of it being associated with an AE/SAE within 24 hours of Investigator's awareness.

Table 10-1 Guidance for capturing the study treatment errors including misuse/abuse

Treatment error type	Document in Dosing CRF (Yes/No)	Document in AE eCRF	Complete SAE form
Unintentional study treatment error	Yes	Only if associated with an AE	Only if associated with an SAE
Misuse/Abuse	Yes	Yes	Yes, even if not associated with a SAE

For more information on AE and SAE definition and reporting requirements, please see the respective sections.

10.2 **Additional Safety Monitoring**

Not applicable.

11 **Data Collection and Database management**

11.1 **Data collection**

Designated investigator staff will enter the data required by the protocol into the Electronic Case Report Forms (eCRF). The eCRFs have been built using fully validated secure webenabled software that conforms to 21 CFR Part 11 requirements. Investigator site staff will not be given access to the EDC system until they have been trained. Automatic validation programs check for data discrepancies in the eCRFs, allow modification and/or verification of the entered data by the investigator staff.

The investigator/designee is responsible for assuring that the data (recorded on CRFs) (entered into eCRF) is complete, accurate, and that entry and updates are performed in a timely manner. The Investigator must certify that the data entered are complete and accurate.

After final database lock, the investigator will receive copies of the participant data for archiving at the investigational site.

All data should be recorded, handled, and stored in a way that allows its accurate reporting, interpretation, and verification.

11.2 Database management and quality control

Novartis personnel (or designated CRO) will review the data entered by investigational staff for completeness and accuracy. Electronic data queries stating the nature of the problem and requesting clarification will be created for discrepancies and missing values and sent to the investigational site via the EDC system. Designated investigator site staff are required to respond promptly to queries and to make any necessary changes to the data.

Concomitant treatments and prior medications entered into the database will be coded using the World Health Organization (WHO) Drug Reference List, which employs the Anatomical Therapeutic Chemical classification system. Medical history/current medical conditions and adverse events will be coded using the Medical Dictionary for Regulatory Activities (MedDRA) terminology.

Laboratory samples will be processed centrally and the results will be sent electronically to Novartis.

Enrollment and data about all study treatment(s) dispensed to the participant will be tracked using an IRT. The system will be supplied by a vendor, who will also manage the database. Novartis may request to receive the IRT data electronically at specific timelines.

Once all the necessary actions have been completed and the database has been declared to be complete and accurate, it will be locked and made available for analysis. Any changes to the database after that time can only be made after written agreement by Novartis development management.

11.3 Site monitoring

Before study initiation, at a site initiation visit or at an investigator's meeting, a Novartis representative will review the protocol and data capture requirements (i.e. eCRFs) with the investigators and their staff. During the study, Novartis employs several methods of ensuring protocol and GCP compliance and the quality/integrity of the sites' data. The field monitor will visit the site to check the completeness of participant records, the accuracy of data capture / data entry, the adherence to the protocol and to Good Clinical Practice, the progress of enrollment, and to ensure that study treatment is being stored, dispensed, and accounted for according to specifications. Key study personnel must be available to assist the field monitor during these visits. Continuous remote monitoring of each site's data may be performed by a centralized Novartis CRA organization. Additionally, a central analytics organization may analyze data & identify risks & trends for site operational parameters, and provide reports to Novartis clinical teams to assist with trial oversight.

The investigator must maintain source documents for each participant in the study, consisting of case and visit notes (hospital or clinic medical records) containing demographic and medical information, laboratory data, electrocardiograms, and the results of any other tests or assessments. All information on CRFs must be traceable to these source documents in the participant's file. The investigator must also keep the original informed consent form signed by the participant (a signed copy is given to the participant).

The investigator must give the monitor access to all relevant source documents to confirm their consistency with the data capture and/or data entry. Novartis monitoring standards require full verification for the presence of informed consent, adherence to the inclusion/exclusion criteria, documentation of SAEs, and of data that will be used for all primary variables. Additional checks of the consistency of the source data with the CRFs are performed according to the study-specific monitoring plan. No information in source documents about the identity of the participants will be disclosed.

12 Data analysis and statistical methods

The analysis will be conducted on all participant data at the time the trial ends. Any data analysis carried out independently by the Investigator should be submitted to Novartis before publication or presentation.

Amended Protocol Version 03 (Clean)

Categorical variables will be presented as counts and percentages. For continuous variable, mean, standard deviation, minimum, 25th percentile, median, 75th percentile, and maximum will be presented.

All summaries will be presented by study arm.

12.1 Analysis sets

The Safety Set comprises all participants who received at least one dose of study drug.

The Safety Set will be used for the summary of demography and baseline characteristics as well as for all safety analyses.

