6.1 Study Treatment

6.1.1 Investigational and control drugs

Novartis will supply the following study treatments:

- Amended Protocol Version 03 (Clean)
- Open-label of atumumab will be provided in an auto-injector containing 20 mg sc ofatumumab (20 mg/0.4ml) for subcutaneous administration.
 - Novartis will supply participants in Cohort 1 with of atumum ab treatment in the Investigational Period and the optional 6-month Extension Period as per the assessment schedule in Table 8-1.
 - Participants in Cohort 2 will continue on their commercially prescribed of atumumab treatment during the Investigational Period. Novartis will supply participants in Cohort 2 with of atumumab treatment in the optional 6-month Extension Period as per the assessment schedule in Table 8-2. Cohort 2 participants may either remain on their prescribed of atumumab or switch to study supplied of atumumab.
- Participants will obtain the quadrivalent influenza vaccine at no cost to them from their local pharmacy using a pharmacy card supplied by Novartis or will receive the vaccine from investigational site supply.

Participants enrolled in Cohort 3 will continue on their commercially prescribed iDMT.

Table 6-1 Investigational and control drugs

	-	~	
Investigational/ Control Drug	Route of Administration	Supply Type	Supplied by
OMB157 20mg/0.4mL	Subcutaneous Use	Open-label commercial supply; vials	Sponsor or commercially prescribed
iDMT	Subcutaneous or intramuscular use	Commercially prescribed	NA
Quadrivalent influenza vaccine	Intramuscular	Commercially supplied	Participants to obtain from their local pharmacy via pharmacy card or from investigational site supply

6.1.1.1 **Decentralized Clinical Trial Model**

The study medication and all required clinical study supplies may be distributed via direct-toparticipant shipment utilizing an extension of the IND for compliance purposes.

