Screening / Pre-vaccine HI titer	Х											
Dispense pharmacy card	S ¹											
IRT transaction	Х	Х	Х	Х	х	Х	Х	Х	Х	Х	Х	
Administration of study drug						Х	Х	Х	Х	Х	Х	
Post vaccine Serum HI titers					X ²							
Drug Accountability Log	S				S			S			S	
Adverse Events / Serious Adverse Events	Х	Х	Х	Х	Х	Х	Х	Х	Х	Х	Х	Х
Subject disposition	Х				Х						Х	

Period	Screening		Investiga	ational Pe	riod		Unscheduled					
Visit Name	Visit 1 Screening	Visit 2 (vaccine status check- in)	Visit 3 (home visit)	Visit 4 (home visit)	Visit 5 EOS1	Visit 6 (home visit)	Visit 7 (home visit)	Visit 8	Visit 9 (home visit)	Visit 10 (home visit)	Visit 11 EOS2	Unscheduled
Day/Week/Month	Week -1	Week 0	Week 1	Week 2	Week 4	Week 8	Week 12	Week 16	Week 20	Week 24	Week 28	
Visit Window Days (d)			± 3d	± 3d	± 3d	± 3d	± 3d	± 3d	± 3d	± 3d	± 3d	
Remote Contact		X ³	S ⁴	S ⁴		S ⁴	S ⁴		S ⁴	S ⁴		

X = assessment to be recorded in the clinical database or received electronically from a vendor

S = assessment to be recorded in the source documentation only

¹ Participants will use the pharmacy card to cover the cost of the influenza vaccine. Participants administered the vaccine from investigator site supply will not receive a pharmacy card. All participants should receive the vaccine within 9 calendar days after the Screening Visit, before the Week 0 visit occurs.

² Post vaccine titer to be drawn before administration of ofatumumab.

³ Remote contact to perform Vaccine Status Check-in by site staff to confirm participant has received the influenza vaccine and to collect any AEs/SAEs.

⁴ Remote contact with participants by site staff. The contact should query about any new AEs or SAEs, changes in con meds and compliance with current treatment. Method of contact can be via telephone, email or text message depending on the preference of each participant

Novartis

Period	Screening Investigational Period							
Visit Name	Visit 1 Screening	Visit 2 (vaccine status check-in)	Visit 3 (home visit)	Visit 4 (home visit)	Visit 5 (home visit)	Visit 6 EOS	Unscheduled	
Day/Week/Month	Week -1	Week 0	Week 1	Week 2	Week 3	Week 4		
Visit Window Days (d)			± 3d	± 3d	± 3d	± 3d		
Obtain informed consent	Х							
Inclusion/exclusion criteria	X							
Demography	X							
Relevant medical history/current medical history	Х							
Prior/Concomitant Medications	X		Χ	Χ	X	Χ	X	
MS Relapse	Х		Х	X	Х	X	Х	
Local Serum Pregnancy Test	S							
Screening / Pre-vaccine HI titer	Х							
Dispense pharmacy card	S ¹							

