DMS Document Management System EMA European Medicines Agency

EOS End of Study
FAS Full Analysis Set

GPS Global Statistical and Programming Environment

HI Hemagluttination Inhibition

IA Interim Analyses
MS Multiple Sclerosis

MedDRA Medical Dictionary for Drug Regulatory Affairs

NRI Non-responder Imputation

PK Pharmacokinetics

PRO Patient-reported Outcomes

PT Preferred Term

QIV Quadrivalent inactivated influenza vaccine

RAP Reporting & Analysis Process
RMS Relapsing Multiple Sclerosis
SAE Serious Adverse Event
SAF Safety Analysis Set
SAP Statistical Analysis Plan
SAS Statistical Analysis System

sc Subcutaneous

SOC System Organ Class

TEAE Treatment Emergent Adverse Events

TFLs Tables, Figures, Listings

iDMT Injectable Disease Modifying Therapy

1 Introduction

The purpose of this Statistical Analysis Plan (SAP) is to describe the statistical methods planned in Section 12 of the Clinical Study Protocol (CSP) version 00 (release date 10 November 2020) for the clinical trial COMB157GUS12 and any additional analyses, specifications or deviations from this planned protocol before clinical database lock (CDBL).

This SAP will be used to draft the Clinical Study Report (CSR) Section 9.7: Statistical methods and IA plans.

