2.2 Analysis sets

Safety set

The Safety Set (SAF) comprises all participants who have received the 2020-2021 inactivated influenza vaccine.

Unless stated otherwise, the SAF will be used for all summary tables and listings.

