2.14 Interim analysis

For the purpose of earlier dissemination of results, an interim analysis will be performed after:

- all enrolled participants have completed the Investigational Period or discontinued the Investigational Period prematurely OR
- On/around March 29, 2021, whichever comes first.

Since there will be no hypothesis testing involved, statistical adjustment for the interim analysis will not be made at the stage of final analyses.

3 Sample size calculation

Sample size calculations were based on the proportion of participants who responded to influenza vaccination.

The sample size of 20 participants per arm is selected based on budget and need for early availability of results. The sample size of 20 subjects will provide estimates with margin of error (half-width of a 95% confidence interval) of 20.1%, 19%, and 17.5% corresponding to response rates of 70%, 75%, and 80%, respectively. Adjusting for 10% drop-out, 22 subjects will be enrolled in each arm.

4 Change to protocol specified analyses

There are no changes to protocol specified analyses.

5 Appendix

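### Protocol 12.1 and SAP 2.2 give the Safety Set different entry rules, and on the protocol's usual meaning of 'study drug' Cohort 3 would leave the demography, baseline and safety tables

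*Protocol*

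**What the plan says.** Protocol 12.1 names one analysis set: "The Safety Set comprises all participants who received at least one dose of study drug". It then gives the set its uses: "The Safety Set will be used for the summary of demography and baseline characteristics as well as for all safety analyses". Protocol 12.4, on the primary endpoint, names no analysis set.

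SAP 2.2 has a set with the same name and a different rule: "The Safety Set (SAF) comprises all participants who have received the 2020-2021 inactivated influenza vaccine". Its reach is wider: "Unless stated otherwise, the SAF will be used for all summary tables and listings". SAP section 4 says: "There are no changes to protocol specified analyses". The SAP introduction ties the plan to protocol version 00 of 10 November 2020; the protocol supplied is Amended Version 03.

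The exclusion tables in SAP 5.4 add further conditions. Participants leave the set for lack of vaccination. They also leave it for study treatment not taken, against deviations INCL06A (Cohort 1 not planning ofatumumab), INCL06B (Cohort 2 not on commercial ofatumumab for at least 4 weeks) and INCL07 (Cohort 3 not on iDMT). INCL05 is worded for the 2020-2021 vaccine only.

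**The concern.** Two sets share a name but not a membership rule. The protocol's rule depends on 'study drug', a term with no glossary entry of its own. If it means ofatumumab, the reference cohort on iDMT disappears from the tables that describe the participants and their safety. So do adverse events after vaccination in Cohort 1 participants who leave before their first ofatumumab dose. If it means any investigational, control or background drug, nobody need be lost, but participants in Cohorts 2 and 3 qualify through therapy they were already taking, vaccinated or not. Neither meaning gives the SAP's rule.

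The SAP's rule is not safe as worded either. It is limited to one season, while the protocol now enrols over three. Correcting the season in the SAP would leave Protocol 12.1 as it is.

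**Working it through.** **1. What 'study drug' means in the protocol.**

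Places pointing to ofatumumab:
- Table 6-2 lists interferon beta and glatiramer acetate among treatments not permitted together with study drug. Sections 1.1 and 4.3 name these as the iDMTs of the reference cohort.
- The row "Administration of study drug" is marked from Week 2 in Table 8-1 (Cohort 1) and only from Week 8 in Table 8-2 (Cohort 2). Table 8-3 (Cohort 3) has no such row and carries an iDMT log instead.
- Section 6.7.2 uses the term for what Cohort 2 is supplied with in the Extension Period. Section 9.1.1 reconciles dispensed study drug for Cohorts 1 and 2 only.
- Section 6.1.1, after listing what the sponsor supplies, says: "Participants enrolled in Cohort 3 will continue on their commercially prescribed iDMT".

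Places pointing to a wider meaning:
- The glossary describes a control drug as a kind of study drug, and section 4.3 discusses iDMT under choice of control drugs.
- Table 6-1 lists iDMT, the vaccine and OMB157 (including commercially prescribed supply) as investigational or control drugs.
- Table 6-3 places iDMT in its investigational-drug column.

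The first group predominates in the operational text. The second prevents calling the usage uniform.

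**2. Inputs.** The plan states no size for the Safety Set. Its enrolment figure reproduces: 20 per arm × 1.10 = 22, and 3 × 22 = 66 (Protocol sections 5 and 12.8.1). Let *x* be the number in Cohort 2 who enter the optional extension and take study-supplied ofatumumab. Section 3 lets them stay on commercial supply, and the documents do not give *x*, so it runs from 0 to 22.

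**3. Planned set under each rule (Cohort 1 + Cohort 2 + Cohort 3).**

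| Rule | Count | Share of 66 |
|---|---|---|
| (a) Study-supplied ofatumumab | 22 + *x* + 0 = 22 to 44 | 33.3% to 66.7% |
| (b) Ofatumumab from any source | 22 + 22 + 0 = 44 | 66.7% |
| (c) Glossary and Table 6-1 meaning | 22 + 22 + 22 = 66 | 100% |
| (d) SAP 2.2 rule, any study season | up to 66 | up to 100% |
| (e) SAP 2.2 as worded | those given the 2020-2021 vaccine | not stated |

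Under (a) and (b) the Cohort 1 figure of 22 is a maximum: each participant vaccinated but gone before Week 2 reduces it by one. That number is not given.

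**4. Loss.** Cohort 3 is lost under (a) and (b): 22/66 = 33.3%. Cohort 2 is reduced only under (a), by 22 − *x*, which is 0 to 22. The total loss under (a) is therefore 22 to 44 of 66, before any early Cohort 1 departures.

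**5. Which outputs.** Protocol 12.1 governs demography, baseline and safety. The primary rate gets its set only through the SAP default, and the SAP set requires vaccination.

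**The case against.** The strongest reply is that the protocol can be read so that nobody is lost. Its glossary and Tables 6-1 and 6-3 bring iDMT and commercial ofatumumab under the heading of trial drugs. Section 12 calls for summaries by study arm, 12.5.2 for safety tables by treatment arm, and 12.8.1 plans 22 in each arm; a set that deletes an arm fits none of these. SAP 5.4 attaches failure to take study treatment to the deviations on commercial ofatumumab and iDMT, which suggests that the SAP counts both as study treatment. Season wording aside, SAP 2.2 keeps all three cohorts, and the study is descriptive with no hypothesis tests.

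Much of this stands. A reader might infer that the protocol plainly excludes Cohort 3 and part of Cohort 2. The documents do not support that: the exclusion follows on one well-supported reading, and the Cohort 2 loss needs the narrowest form of it.

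A reader might also infer that unvaccinated participants, imputed as non-responders, would lower the primary seroprotection rate. Neither document produces this. Protocol 12.1 does not apply its set to the primary endpoint, and the SAP set already leaves out the unvaccinated.

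Nor can it be shown that the no-changes statement in SAP section 4 was wrong when written, since version 00 is not supplied. The amendment summaries mention no change to the analysis set, so the mismatch may be old, but that is inference.

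The reply does not remove the conflict. The wide reading makes membership independent of vaccination, which is not the SAP's rule, and SAP 5.4 shows that the SAP's own rule is not vaccination alone.

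**Conclusion.** The point holds in limited form. The two documents define the Safety Set by different rules, the protocol's rule rests on an undefined term, and the difference from the current protocol is not declared. On the predominant operational meaning of that term, all 22 Cohort 3 participants, any Cohort 1 participant vaccinated but gone before Week 2, and (if only study-supplied drug counts) 0 to 22 Cohort 2 participants would be missing from the demography, baseline and safety tables. The set would then be 22 to 44 of 66. On the wide meaning it could be all 66, without regard to vaccination.

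These counts assume full planned enrolment, every Cohort 1 participant dosed, and an unknown number in Cohort 2 taking study supply. No effect on the primary rate is shown. The matter still needs settling before database lock, because the rule as written can remove the reference cohort from the safety tables and the SAP's rule, read literally, covers one season of three.

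**What to change.** Put one definition in Protocol 12.1 and SAP 2.2: *all participants who received the study influenza vaccine (2020-2021, 2021-2022 or 2022-2023), analysed by cohort*. State in both that this set is used for the baseline, safety and immunogenicity analyses. The SAP default already implies this; the protocol names no set for immunogenicity.

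In the same edit, reconcile the SAP 5.4 exclusion tables with the new sentence:
- decide whether a vaccinated participant is still removed for study treatment not taken under INCL06A, INCL06B and INCL07;
- extend the wording of INCL05 to all three seasons.

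Update the SAP's protocol reference, and its section 4 if any difference remains. The cost is a few sentences in the two documents and edits to the SAP exclusion tables. No extra data are needed, since the Week 0 check already confirms vaccination and participants are asked for pharmacy documentation.
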